5.2 Prior and concomitant medications/non-drug therapies

Prior and concomitant medications will be coded according to the World Health Organization-Drug Dictionary (WHO-DD). The WHO-DD version will be specified as a footnote in the tables/listings. Prior and concomitant medications are mutually exclusive, as defined below:

- Prior medications are defined as any medications with an end date prior to the first dose of BGJ398;
- Concomitant medications are defined as any medications taken during the treatment period (from the first dose date and on). Prior medications that are ‘ongoing’ at the time of first study treatment or whose end date is after first study treatment will be considered concomitant medication.

The number and percentage of subjects with prior medications, concomitant medications that started prior to BGJ398 initiation, as well as concomitant medications that started after BGJ398 initiation, will be summarized by preferred term. Non-drug therapies (surgical and medical procedures) will be listed for each subject. A standard imputation method will be used for partial start/stop date of medications.

6 Efficacy and PRO evaluation

6.1 Clinical Benefit Rate (CBR)

Clinical benefit is determined by investigator assessment for each tumor assessment and is defined as responses of CR or PR or SD \geq 16 weeks. For subjects with TIO diagnosis without measureable/evaluable disease, the following criteria will be used to determine the assessment at 16 weeks:

- the tumor associated changes of metabolic parameters: plasma level of FGF23 < or =180 RU/mL; and inorganic phosphorous, calcium, and 1-25-dihydroxy vitamin D greater than the lower limit of normal (LLN) (20%); and
- without requirement of supplementation therapy for at least the preceding cycle of the 16 week assessment.

Subjects with TIO diagnosis, but having known underlying tumor/disease type, their tumor response summaries will be treated same as for subjects with the same underlying tumor type.

In addition to tumor-specific measurements (e.g., radiological assessment of tumor response for solid tumors), progressive disease will also be considered when it was indicated either as a reason based on clinical assessment for the study treatment discontinuation or as a cause of on-treatment death. CR and PR (for solid tumors) require a confirmation that is at least a minimum of 4 weeks after the initial observation of response. Subjects who had confirmed CR/PR or SD prior to 16 weeks, but discontinued prior to 16 weeks for reasons other than

progressive disease, will have their clinical benefit defined as non-evaluable; subjects who had confirmed CR/PR or SD prior to 16 weeks, but progressed prior to 16 weeks, will be considered as not achieving clinical benefit; subjects who had CR/PR/SD occurred prior to 16 weeks, but progressed at or after 16 weeks without evidence of CR/PR/SD at or after 16 weeks, will also be considered as not achieving clinical benefit. CBR will be analyzed by comparing achieved CBR with a historical control rate of each tumor type, and if there is at least 90% probability that the response rate in a tumor type exceeds the historical rate, then the tumor type will be considered a success; it will be considered as promising if the probability is between 80% and 90%. Details for the analyses of CBR are located in Section [Error! Reference source not found.](#)

6.2 Overall Response Rate (ORR)

Overall response is determined by investigator assessment for each tumor assessment in the study. For subjects with solid tumors (other than lymphoma) the assessment criteria will be RECIST 1.1 and will include responses of CR and/or PR; for lymphoma, Cheson criteria will be used; for hematologic tumors, other appropriate hematological response criteria will apply. The number and percentage of subjects for different categories of overall response (e.g., for solid tumors – CR, PR, SD, PD, Not Evaluable) will be provided for solid tumors (non-lymphoma), lymphoma (if applicable), and each hematological tumor type (if applicable). Ninety-five percent (95%) exact confidence intervals (CIs) will be provided for the response rate(s) (e.g., for solid tumors – CR and/or PR) as well. For cohorts with at least 10 subjects, overall responses will be summarized separately. Components of tumor assessments (e.g., for solid tumors – target lesion response, non-target lesion response, new lesion [yes/no]) will also be listed. In addition, Cancer Antigen-125 (CA-125) (if applicable) in the assessment of ovarian cancer response, Prostate-specific Antigen (PSA) (if applicable) in the assessment of prostate cancer will be listed.

The above analyses will be performed for the FAS.

6.3 Progression Free Survival (PFS)

PFS is defined as the time from the date of first dose of BGJ398 to the date of the first documented disease progression/relapse or death due to any cause within 30 days of the last dose, and is calculated as $PFS = (\text{date of progression/relapse or death} - \text{date of first study treatment} + 1)$. Disease progression noted as the reason for discontinuation of treatment will be considered as a progression, thus will be considered as an event for PFS.

Subjects who discontinue or complete study treatment without disease progression will be censored at last adequate tumor assessment on or before the discontinuation/completion of the study. For subjects who are still on study treatment at the time of data cut-off date for the primary analyses, PFS will be censored at the last adequate tumor assessment before the data cut-off date for the analysis of PFS on the primary CSR. For subjects who have no tumor assessment post baseline, PFS will be censored at Day 1. The final CSR (i.e., addendum to the primary CSR) will utilize additional PFS data obtained from these subjects after the primary CSR cut-off date.

PFS will be summarized and graphed using the Kaplan-Meier product-limit method¹. The estimated median survival time, the corresponding 95% CIs², and 25th and 75th percentiles will be provided. In addition, survival rate estimates at 1, 2, 3, 4, 5, 6, and 12 months with 95% CIs will also be provided. For cohorts with at least 10 subjects, separate PFS analyses will be conducted for each cohort.

The above analyses will be performed for the FAS.

6.4 Overall Survival (OS)

Overall survival, defined as the time from the date of the first dose of BGJ398 to the date of death will be analyzed using methods similar to those stated above for PFS. That is, 25th percentile, median, and 75th percentile of survival time with corresponding 95% CIs will be provided; survival curve and survival rates at 3, 6, 12, 18, and 24 months will also be presented. Subjects who are alive at the time of discontinuation/completion of the study will be censored at the last contact date or end of treatment visit date if the subject elected not to be followed post study treatment. If the subject is still being followed in the study as of the data cut-off date for the primary CSR, the subject will be censored at the data cut-off date. For groups with at least 10 subjects, separate OS analyses will be conducted for each group. The final CSR (i.e., addendum to the primary CSR) will utilize additional survival data obtained from these subjects after the primary CSR cut-off date.

The above analyses will be performed for the FAS.

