4.2 Definition of end of the study

End of study is defined as the time when the last patient completes survival follow-up as described in [Section 7.1.4.3](#), or when the last patient on study has died, been lost to follow up or withdraws consent, or when the study is terminated early, whichever occurs first.

The analysis of study data will be based on all patients' data up to the time when all patients have had the opportunity to complete at least 4 cycles (or 16 weeks) of treatment or discontinued the study. This will be the cut-off point for the primary clinical study report (CSR). Additional data for patients continuing to receive study treatment past the data cutoff

date for the primary CSR will be reported once all patients have discontinued treatment or been lost to follow-up. It will be reported in an addendum to the CSR, as appropriate.

At the time of CSR data cut-off, if patients are ongoing after 16 weeks on treatment and benefitting, they will continue to receive treatment, every effort will be made to continue provision of study treatment outside this study through an alternative setting to patients who in the opinion of the investigator are still deriving clinical benefit and the Novartis therapy is not commercially available and reimbursable.

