7.1.4.3 Survival follow-up

Survival information will be collected, only for six tumor types that are listed in the inclusion criteria, every 3 months until 2 years after the last patient has enrolled in the study regardless of treatment discontinuation reason (except if consent is withdrawn). If the study primary efficacy endpoint is not met, Novartis may decide not to conduct survival follow-up for the study. Additional survival assessments may be performed outside the 3 months follow-up schedules if a survival update is required for an interim assessment to meet safety or regulatory needs.

Survival information can be obtained via phone, and information will be documented in the source documents and relevant eCRFs.

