10.4.4 Handling of missing values/censoring/discontinuations

A patient who has not progressed or died at the date of the analysis cut-off would have his/her PFS and OS censored at the time of the last adequate assessment before the cut-off date. Any disease assessment indicating response status other than “unknown” or “not done” is considered an adequate response assessment.

No imputation of missing values will be performed on any of the efficacy endpoints.

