10.5.2 Other secondary efficacy objectives

The secondary efficacy objectives of the study:

- To assess progression free survival (PFS) based on local investigator assessment per RECIST 1.1 or other appropriate hematological response criteria
- To assess overall survival
- To assess duration of response (DOR) based on local investigator assessment per RECIST 1.1 or other appropriate hematological response criteria

The secondary efficacy variable progression free survival (PFS) is defined as the time from the date of first dose to the date of first documented disease progression or relapse or death due to any cause.

PFS will be summarized and graphed using the Kaplan-Meier product-limit method for each patient group. Patients who drop-out without progression will be censored at the time of last adequate assessment. The estimates of the 25th, median, 75th percentiles of the PFS and their 95% confidence intervals will be provided, if applicable.

Overall survival (OS) is defined as the time from the date of first dose to the date of death due to any cause. If a patient is not known to have died, survival time will be censored at the date of the last contact.

OS will be summarized and graphed using the product-limit method as above.

The duration of response (PR or greater) applies only to patients whose best response was PR or greater. For patients with solid tumors the assessment criteria will be RECIST 1.1 and will include responses of CR and/or PR. For hematologic tumors other appropriate hematological response criteria will apply and are included in the appendices. The duration of response is defined as the time from the first documented response to the date first documented disease progression or relapse or death due to any cause. The duration of response will be summarized descriptively for each patient group.

If the study primary efficacy endpoint is not met, Novartis may decide not to conduct some of the above secondary efficacy analyses but instead provide those endpoints in listings only.

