Exploratory mutation profile analyses will be conducted by a Novartis computational biologist.

All other data will be analyzed by a different Novartis-designated CRO, [REDACTED] [REDACTED] according to Section 10 of the study protocol which will be available in Appendix 16.1.1 of the Clinical Study Report (CSR). Important information is given in the following sections and details will be provided, as applicable, in Appendix 16.1.9 of the CSR. All statistical analyses will be performed using SAS® Version 9.3 (or higher).

2 Statistical and analytical plans

Data from all centers that participate in this protocol will be used. Per protocol, the analyses stated in this document will be based on all subjects' data up to the time when all subjects have had the opportunity to complete at least 4 cycles (or 16 weeks) of study treatment or all subjects have discontinued study treatment, whichever is first. All subjects will be followed for survival status every 3 months for 2 years after the last subject has enrolled in the study regardless of treatment discontinuation reason (except if consent is withdrawn or patient is lost to follow-up). However, as most subjects have been discontinued study treatment, the primary CSR analyses will be conducted after last patient discontinues study treatment.

All statistical analyses presented in this document are related to subject background information, efficacy, and safety variables collected for the study. All analyses are descriptive and no hypothesis testing is planned (except for the primary efficacy variable, which is described in Section **Error! Reference source not found.**). Data from all centers will be combined for any analysis. In general, there is no stratification factor being considered for the analysis with the exception of tumor type in the primary efficacy variable analyses. Missing data will not be imputed unless otherwise specified. All data collected in the study will be presented in the listings. In general, this document will detail the methods used in summaries/tabulations.

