Subjects are administered with BGJ398 at 125 mg once daily, 3 weeks on 1 week off. A complete treatment cycle is defined as 28 days. Subjects may continue on study treatment until disease progression, withdrawal of consent, unacceptable toxicity, death, or any other reasons (e.g., physician's decision). After discontinuation of study treatment, subjects, regardless of reason for study treatment discontinuation will be followed for safety for 30 days after the last dose. Survival information will be collected every 3 months until 2 years after the last subject has enrolled in the study regardless of treatment discontinuation reason (except if consent is withdrawn). If the study's primary efficacy endpoint is not met, Novartis may decide not to conduct survival follow up for the study. Additional survival assessments may be performed outside the 3 months follow-up schedules if a survival update is required for an interim assessment to meet safety or regulatory needs.

The primary efficacy objectives of the study, clinical benefit (definition details see Section 6.1) associated with BGJ398 treatment based on local investigator assessment, will be summarized. The clinical benefit rate will be analyzed using a Bayesian hierarchical model to evaluate trial success and futility, and the relationship between relevant pathway regulation and the response to treatment with BGJ398 (if applicable). Analysis details are documented in Section **Error! Reference source not found.**

Duration of response (DOR) based on local investigator assessment will be analyzed. In the event of a low response rate, DOR will be listed only without frequency summaries. Overall response (OR) will be summarized with the number and percentages of subjects for each response category (e.g., for solid tumor - CR, PR, SD, PD, Not evaluable). Progression-free survival (PFS) and overall survival (OS) will be summarized using Kaplan-Meier (KM) methodology.

Subject demographics, disease characteristics (including mutation analyses), BGJ398 treatment, and safety variables will be summarized descriptively, by nominal visit (if applicable), and/or overall.

Data used for the analyses specified in this document will come from the Electronic Data Capture (EDC) system. In addition, the mutation data from the central laboratory will be collected in an Excel spreadsheet format and subsequently be uploaded to a secure FTP site by Novartis.

[figure not shown]

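### The protocol and SAP give different OS censoring dates for subjects still followed at the data cut-off, and the cut-off date is unclear; the effect on OS is small

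*SAP*

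**What the plan says.** **Three censoring rules**

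- Protocol 10.4.4: "A patient who has not progressed or died at the date of the analysis cut-off would have his/her PFS and OS censored" at the last adequate assessment before the cut-off. The next sentence explains adequacy in terms of a disease assessment.
- Protocol 10.5.2: for a patient not known to have died, "survival time will be censored at the date of the last contact".
- SAP 6.4: subjects alive when they leave or complete the study are censored at last contact, or at the end-of-treatment visit if they declined follow-up. For a subject still followed at the cut-off "for the primary CSR, the subject will be censored at the data cut-off date".

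SAP 2.1, which lists changes from the protocol, covers PFS, duration of response and vital signs but not OS censoring.

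**Survival contacts.** SAP 2: "Survival information will be collected every 3 months until 2 years after the last subject has enrolled in the study". Protocol 7.1.4.3 narrows this: "Survival information will be collected, only for six tumor types that are listed in the inclusion criteria". Off-schedule contact is optional: "Additional survival assessments may be performed outside the 3 months follow-up schedules if a survival update is required for an interim assessment" for safety or regulatory needs. Phone contact is allowed.

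**Cut-off.** Protocol 4.2 places the primary CSR cut-off when all patients have had the opportunity for 16 weeks of treatment or have discontinued. SAP 2 first repeats this, taking whichever comes first, and then says "the primary CSR analyses will be conducted after last patient discontinues study treatment". SAP 6.3 still provides for subjects on treatment at the cut-off.

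**The concern.** Two programmers working from these texts could derive different OS times for the same subject. The SAP rule also credits survival that nobody has checked. With contacts 3 months apart, a subject may have died after the last contact and still be counted as alive to the cut-off. Last contact carries the opposite risk. If sites report deaths as they occur while survivors count only to their last scheduled contact, deaths are observed over a longer window than survival. A rule tied to the cut-off date also needs that date to be unambiguous. What is at stake is the Kaplan-Meier median and the 18- and 24-month OS rates, overall and in groups of at least 10 subjects.

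**Working it through.** The documents give no OS assumption, event count or power, so there is no plan figure to reproduce.

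**1. One subject, three dates.** Assume a subject stops treatment without progression on day 140, has a last adequate scan on day 113 (week 16), is contacted every 91 days from end of treatment, reaches the cut-off on day 400, and is not known to have died. Contacts fall on days 140, 140 + 91 = 231 and 231 + 91 = 322; the next would be day 413.

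| Rule | OS censored at |
|---|---|
| Protocol 10.4.4 | day 113 |
| Protocol 10.5.2 | day 322 |
| SAP 6.4 | day 400 |

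The SAP rule credits 400 − 322 = 78 unverified days here, and at most about 91. If the same subject had progressed, 10.4.4 would not apply on its wording, leaving day 322 against day 400. If the subject had left the study alive, 10.5.2 and SAP 6.4 would largely agree.

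**2. Size, by simulation.** Assumptions, none of them from the documents except the contact and scan intervals and the 2-year enrolment period: exponential OS with median 4, 6, 9 or 12 months; median time on treatment 3 months; uniform accrual over 24 months; 3-monthly contacts from end of treatment; scans at weeks 8 and 16, then every 16 weeks; cut-off 16 weeks or 9 months after last enrolment; 400,000 subjects per setting. Unless stated otherwise, a death after treatment is learned at the next scheduled contact.

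Let C be the cut-off and L the last scheduled contact on or before C. The SAP rule counts a death at time T if T ≤ C and it is learned by lock, and otherwise censors at C. Protocol 10.5.2 with prompt reporting counts T ≤ C and censors survivors at L. The single-date rule counts T ≤ L and censors at L.

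Kaplan-Meier medians in months, for true medians 4 / 6 / 9 / 12:

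| Rule | Cut-off at 16 weeks | Cut-off at 9 months |
|---|---|---|
| SAP 6.4, lock at cut-off | 4.06 / 6.16 / 9.38 / 12.67 | 4.00 / 5.99 / 9.05 / 12.29 |
| SAP 6.4, lock 1 month later | 4.02 / 6.06 / 9.16 / 12.27 | 4.00 / 5.99 / 9.00 / 12.12 |
| SAP 6.4, lock 3 months later | 4.00 / 6.00 / 9.00 / 12.00 | 4.00 / 5.99 / 8.99 / 12.01 |
| Protocol 10.5.2, deaths reported at once | 3.96 / 5.87 / 8.70 / 11.47 | 4.00 / 5.99 / 8.94 / 11.79 |
| Deaths and survivors both through L | 4.00 / 6.00 / 9.00 / 12.00 | 4.00 / 5.99 / 8.99 / 12.01 |
| Protocol 10.4.4, applied to everyone not known dead | 3.60 / 4.81 / 6.22 / 7.35 | 3.82 / 5.27 / 6.90 / 8.07 |

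The largest upward shift is 12.67 − 12 = 0.67 months and the largest downward shift under 10.5.2 is 12 − 11.47 = 0.53 months. At lock on the cut-off date, 1.5% to 3.7% of subjects have died unseen. For a true median of 9 months and the earlier cut-off, true 24-month OS is 0.157; the SAP rule gives 0.198 with lock at cut-off and 0.157 with lock 3 months later, and 10.5.2 with prompt deaths gives 0.124. The 10.4.4 row is an outer bound, because that text covers only patients without progression.

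**3. Scale.** For 90 patients and a true median of 9 months, SE(median) ≈ 1 / (2 f √n), with f = 0.5 × ln 2 / 9 = 0.0385. This gives 1 / (2 × 0.0385 × 9.49) = 1.37 months, so sampling error alone spans about 9 ± 1.96 × 1.37, or 6.3 to 11.7 months.

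**The case against.** The strongest reply is that the conflict is narrow and its effect slight.

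- A reader might infer that every subject's OS has three competing dates. The documents do not support that. Protocol 10.4.4 is a joint PFS/OS sentence limited to patients who have not progressed or died, and SAP 6.4 does not use it.
- A reader might infer that the SAP rule inflates OS. It does so only while deaths before the cut-off are unknown at lock. Protocol 9.4 requires deviation review and data verification before lock, so lock on the cut-off date is an upper bound. With prompt reporting of deaths the SAP rule is unbiased; with deaths learned only at contacts, last contact is unbiased. The documents do not say which pattern applies, so the upward and downward figures cannot both hold in the same trial.
- A reader might infer that SAP 2 has moved the cut-off to the last treatment discontinuation. It does not say so. An early data cut-off with a later analysis is a natural reading, and SAP 6.3 fits it. The lag to lock would then often approach or exceed 3 months and the bias would be close to zero.
- If the primary endpoint is not met, survival follow-up may be dropped (Protocol 7.1.4.3, SAP 2) and secondary endpoints may appear in listings only (Protocol 10.5.2). The disputed clause would then matter little.

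All of this stands, and it limits the size of the point. It does not remove the mismatch between the documents, the omission from SAP 2.1, or the missing condition that a subject censored at the cut-off be known alive then.

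**Conclusion.** The mismatch is certain from the text; its severity is minor. The rules conflict only for subjects still followed at the cut-off, three ways if progression-free and two ways if progressed. Under the assumed medians of 4 to 12 months and 3-monthly contacts, the SAP rule shifts the median by 0 to about +0.7 months with lock at the cut-off and by about zero with lock 3 months later. Last contact with prompt death reports shifts it by 0 to about −0.5 months. Both are well inside sampling error. OS is descriptive, the CSR addendum uses later survival data, and no clinical benefit decision changes. Nor do the figures show that a mandatory status check at the cut-off is needed: using the same ascertainment date for deaths and survivors removes the bias without one.

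**What to change.** 1. Delete 'and OS' from Protocol 10.4.4.
2. State the OS data cut-off date, reconciling Protocol 4.2 with the two statements in SAP 2.
3. Put one rule in Protocol 10.5.2 and SAP 6.4, with the same ascertainment date for deaths and survivors:
   - If vital status is updated at the cut-off, count deaths on or before it, censor at the cut-off only subjects confirmed alive on or after it, and censor all others at the last date known alive.
   - If it is not updated, count deaths and censor survivors through the same last scheduled contact on or before the cut-off.
4. List the change in SAP 2.1.

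The cost is text edits in four sections and one derivation. A phone status update at the cut-off is optional and already permitted by Protocol 7.1.4.3. The rule without that update leaves deaths after the last scheduled contact out of the primary CSR until the addendum.
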